14.1 Definitions of safety-related terms

14.1.1 What is an adverse event (AE)?

"Adverse Event (AE)" means any unintended symptom (including symptoms, signs, abnormalities in laboratory test results, etc.), symptoms, or diseases that occur in a subject during a clinical trial and does not necessarily have a causal relationship with the investigational device.

14.1.2 Adverse Device Effect (ADE)

"Adverse Device Effect (ADE)" refers to any harmful and unintended reaction caused by an investigational device and a causal relationship with an investigational device cannot be denied.

14.1.3 Serious AE/Serious ADE

"Serious adverse events, adverse medical device reactions (SDEs)" refers to adverse events or adverse reactions to medical devices used in clinical trials that fall under any of the following:

- 1) In the event of death or danger to life
- 2) Need to be hospitalized or need to extend the length of hospitalization
- 3) Resulting in permanent or significant disability and functional decline
- 4) If the fetus has malformations or abnormalities

Significant medical events that are not immediately life-threatening and do not result in death or hospitalization, but that, based on appropriate medical judgment, require intervention to endanger the subject or prevent the consequences listed in the above definition, should also be considered serious adverse events or adverse medical device reactions. If the subject presents to the emergency department and the treatment time exceeds 24 hours, the admission criteria are considered to have been met, and if the subject is scheduled to be hospitalized before the application of the first investigational device, or in the case of cosmetic plastic surgery, it is not considered as an adverse event, serious adverse event, or adverse reaction to a medical device. Elective surgery in the absence of adverse events and subsequent hospitalization are also not considered serious adverse events or adverse medical device reactions. However, if hospitalization is not planned or is the result of an adverse event, it is considered a serious adverse event or adverse medical device reaction.

Even if it is not the situation listed above, if a situation occurs that is medically considered to have a significant impact on the safety and health status of the subject, the medical judgment of the doctor in charge and relevant experts will determine whether or not to consider it a serious adverse event and take appropriate measures accordingly.

14.1.4 Unexpected ADE

"Unexpected Adverse Device Event" refers to a difference in the aspect or degree of harm of an adverse medical device in light of available medical device-related information such as clinical trial data books or medical device accompanying documents.

14.2 Record of Adverse Events

From the time of application of the investigational device to the date of the last visit, undesirable and unintended symptoms (e.g., abnormalities in laboratory tests), symptoms, and diseases that occur in the subject will be recorded as adverse events. Symptoms, symptoms, or diseases that appeared before the application of the investigational device will only be considered as adverse events if they worsen after the application of the investigational device.

14.2.1 Record of Adverse Events

For all adverse events that occur immediately after the application of the investigational device, the investigator shall record the information in the CRF and medical record using the following guidelines and definitions when reporting the following adverse events.

1) Characteristics of adverse events

: It is preferable to describe a comprehensive diagnosis or syndrome rather than individual symptoms/symptoms. The investigator should report adverse events using standard medical terminology. CRF and supporting documents should be consistent.

2) Manifestation date (start date)

: The date of the start of the adverse event, the date of the test reported as abnormal for clinically significant abnormalities in the laboratory test value

3) Adverse event severity

: If an adverse event occurs, it shall be reported according to the following "Regulations on the Management of Safety Information on Adverse Events of Medical Devices" in accordance with Article 7 (Evaluation Criteria and Evaluation Methods for Adverse Events) Paragraph 1 [Appendix 3] criteria.

Mild	If it does not interfere with the normal daily life (function) of the user of the medical device, causes minimal inconvenience, and can be easily tolerated
Moderate	If it causes inconvenience that significantly interferes with the normal daily life (function) of the user of the medical device
Severe	If it makes it impossible for the user of the medical device to live normally (function)

4) Actions for Investigational devices

: Measures regarding the application of an investigational or control medical device due to the occurrence of an adverse event shall be recorded in the CRF and medical record according to the following classifications.

- A. Not applicable: Adverse events occurring during the non-application period of the investigational or comparator medical device (before and after the treatment period or in the case of single-application clinical trials)
- B. Temporary discontinuation: Temporarily discontinued use of an investigational or comparative medical device due to this adverse event because the subject chooses to discontinue the application of the investigational or comparative medical device, or the investigator determines that discontinuation of the application of the investigational or comparative medical device is the best course of action considering the safety of the subject.
- C. No change in dose: Investigational or comparator medical device application remains the same despite the presence of adverse events
- D. Permanent discontinuation: If the subject chooses to discontinue the application of the investigational or comparative medical device, or if the investigator determines that discontinuation of the investigational or comparative medical device is the best course of action for the subject, and the application of the investigational or comparative medical device is permanently discontinued due to this adverse event

5) Other actions taken

: Regarding the treatment of adverse events, etc., select one of the following items and record it in the CRF and medical record.

- A. None: No other action was taken for this adverse event.
- B. Drug application: For this adverse event, a specific drug (prescription or over-the-counter drug) was applied or the existing drug dose was changed.
- C. Hospitalization or prolonged hospital stay: This adverse event resulted in the subject being hospitalized or the length of hospital stay was prolonged.
- D. Therapeutic or diagnostic procedures: Subjects have utilized other therapeutic means (e.g., ice, electric cushions, orthoses, plaster bandages, etc.) or underwent diagnostic procedures due to this adverse event (e.g., additional laboratory tests, x-rays, etc.).
- E. guitar

6) Loss date (end date)

: Date of extinction of the adverse event. If the adverse event consists of multiple symptoms/symptoms, the duration of the adverse event is determined by the symptom/symptom with the longest duration.

7) result

: Changes in adverse events are judged based on the following criteria.

- A. Recovered: The adverse event no longer exists. (Complete extinction)
- B. Recovering: Subject's condition is improving or symptoms are still residual
- C. Recovered but Aftereffects: Abnormal Damage has been restored, but residual effects still remain.
- D. Non-recovery: If the subject's condition does not recover, and there is no change in symptoms (e.g., atrial fibrillation has become chronic)

E. Death: This adverse event caused the death of the subject or directly caused the death of the subject.

F. Undecidable

8) Evaluation of causal relationships with investigational devices

: In the event of an adverse event, the investigator shall evaluate whether it is related to the investigational device according to the following "Regulations on the Management of Safety Information on Adverse Events of Medical Devices" Article 7 (Evaluation Criteria and Evaluation Methods for Adverse Events) Paragraph 2 [Appendix 3], and the investigator's opinion shall be described. In this case, except for "not related", the rest of the evaluation items are evaluated as having an association with the investigational device.

Relevance Obvious (Definitely related)	The relationship between the occurrence of an adverse event and the use of the medical device is valid, and it is most likely explained by the use of the medical device more than any other reason, and the adverse event symptoms caused by the discontinuation of the use of the medical device disappear, and the adverse event symptoms appear when reuse (performed only when reuse is allowed), and the adverse event that occurs is consistent with information already known about the medical device or the medical device of the same class.
Relevant (Probably related)	There is evidence of the use of the medical device, the temporal sequence of the use of the medical device and the occurrence of the adverse event is reasonable, it is explained more likely by the use of the medical device than by other causes, and the symptoms of the adverse event caused by the discontinuation of the use of the medical device disappear
Doubtful relevance (Possibly related)	There is evidence that the medical device was used, the temporal sequence of the use of the medical device and the occurrence of the adverse event is reasonable, it is determined that the use of the medical device is attributable to the same level as other allowed causes, and the symptoms of the adverse event caused by the discontinuation of the use of the medical device disappear.
Less relevant (Probably not related)	There is evidence of the use of the medical device, there is a more likely cause for the adverse event, the symptoms of the adverse event caused by the discontinuation of the use of the medical device disappear or are ambiguous, and the result of reuse of the medical device (performed only if reuse is allowed) does not show or is ambiguous
Not relevant (Definitely not related)	The medical device was not used, or the temporal sequence between the use of the medical device and the onset of the adverse event was not valid, or there was another obvious cause for the adverse event.
Unassessable (Unknown)	If the information is insufficient or conflicting and cannot be judged, and it cannot be supplemented or verified.

14.2.2 What to do in the event of an adverse event

1) Adverse Case Training

The principal investigator shall educate the investigator and the subject or representative on all adverse events that may occur after the application of the investigational device and report all phenomena that appear after use.

In the event of an adverse event, it is managed so that the necessary examination and treatment can be received immediately from the attending doctor. In the event of a serious adverse event, the clinical trial of the subject shall be stopped and prompt and appropriate measures shall be taken in accordance with "17.3 Reporting of Serious Adverse Events".

2) Follow-up observation of abnormal cases

The investigator shall follow up the subject with an adverse event until the symptoms disappear and the condition stabilizes, and if requested by the sponsor, submit a report on the subsequent progression of the adverse event.

3) Treatment in case of worsening symptoms

: Criteria for subject discontinuation or dropout set forth in "12.1 Discontinuation or dropout of the clinical trial" (2) If the subject is discontinued due to the occurrence of adverse events or serious adverse events that make it difficult to proceed with the clinical trial, the application shall be stopped immediately and replaced with an appropriate treatment regimen to ensure the safety of the subject.

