1.2 Clinical trial Schedule

Visit ± Visit window	Screening1)	Surgery date2)	Follow-up	End of Clinical Trial	Un- scheduled Visit
	Before surgery Within 4 weeks	0 days	3 weeks postoperatively	6 weeks postoperatively	
	Visit 1		Visit 2	Visit 3	
Written informed consent3)	●				
Screening number assignment	●				
Demographic survey4)	●				
Concomitant medication/treatment5)	●	●	●	●	●
Medical history6)	●				
Body Measurement7)	●				
Physical examination8)	●	●	●	●	(●)
Laboratory Tests9)	●	●		●	(●)
Vital signs10)	●	●	●	●	(●)
Evaluation of Inclusion/Exclusion Criteria	●	●			
Randomization		●			
Surgery		●			
Investigational device Application		●			
MRI Scar score11)				●	(●)
100mm-VAS Evaluation (Waist) ¹²⁾		●	●	●	(●)
100mm-VAS Evaluation (Legs) ¹²⁾		●	●	●	(●)
ODI Evaluation12)		●	●	●	(●)
Adverse Event Evaluation		●	●	●	●

* (●) Marks are carried out as necessary according to the judgment of the examiner.

- 1) Screening tests will be performed within 30 days before surgery.
The screening visit (V1) and surgery (V2) can be performed on the same day.
- 2) If the hospital stay is prolonged or severe treatment is required due to the occurrence of surgical complications, it is reported as an SAE.
- 3) Written informed consent must be obtained before clinical trial procedures are performed.
- 4) After obtaining written informed consent, demographic information (sex, age, and reproductive status) will be investigated.
- 5) Prior medications/treatments will be collected for medications administered preoperatively and treatments administered within 4 weeks from the time of V1, and as concomitant medications/treatments if ongoing treatment is required.
- 6) Medical history will include any illness or clinically significant medical condition experienced or ongoing within 12 months at the time of V1.
- 7) Collect height, weight.
- 8) It is collected under the following items: 'appearance', 'skin', 'head/neck', 'heart', 'abdomen', 'urinary/reproductive system', 'limbs', 'musculoskeletal system', 'nervous system', 'lymph nodes', and 'others'.
- 9) The investigator will investigate the following items from the subject's blood and urine at V1, V2, and V4, and if necessary, this test may also be performed at un-scheduled visits at the investigator's discretion. If there is

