12. CRITERIA FOR SUBJECT DISCONTINUATION OR DROPOUT

12.1 Discontinuation or Dropout of the Clinical Trial

If the following cases occur, all or part of the clinical trial sites will review the existence of the clinical trial based on the relevant clinical trial plan.

- 1) If the situation observed during the clinical trial is determined to be unreasonable for the clinical trial to continue, the principal investigator must request the clinical trial review board to stop the clinical trial, and may suspend the clinical trial according to the decision of the clinical trial review board.

- 2) If the subject is discontinued due to the occurrence of an adverse event/serious adverse event that makes it difficult to proceed with the clinical trial (if the investigator determines that the study should be stopped)
- 3) When a change in the clinical trial plan is required, but the site is unable to respond to it
- 4) When the head of the site gives an amendment order based on the opinion of the review committee of the site and the sponsor is unable to approve it,
- 5) If the director of the site orders the suspension of the clinical trial based on the opinion of the institution's review board that the clinical trial cannot be continued.
- 6) If the site has committed serious or continuous violations that are different from KGCP and this clinical trial agreement

In addition, if the sponsor decides to suspend or discontinue the clinical trial, he or she shall promptly notify the Clinical Trial Review Committee and the principal investigator in writing of the purpose and reason. However, if there is a separate notification regulation for suspension or suspension of clinical trials depending on the institution, it shall be followed.

If the principal investigator receives a notice from the sponsor regarding the suspension or suspension of the clinical trial, the principal investigator shall promptly notify the subject of the suspension or suspension of the clinical trial and ensure appropriate treatment and follow-up treatment.

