12.3 Subject dropouts

- 1) If the following are found during surgery
 - A. If there must be other devices left at the surgical site that may interfere with the interpretation of the study results
 - B. If dural rupture and dural hole are found during surgery
 - C. Epidural fat placement
 - D. If you have a herniated disc and need surgery on more than one level
 - E. If you are applying a sealant or making other attempts to repair a fibrous annulus tear
 - F. If a tumor in the spine is found during surgery
 - G. Entering the dura mater during surgery
 - H. If spinal fusion is required
 - I. If the hemostatic agent must remain at the surgical site
, but if it is cleaned after stopping the bleeding, it will not be dropped out.
 - J. If antibiotic powder is injected into the surgical site
(antibiotic cleaning is only allowed before the application of the medical device, not after applicati

on.)

K. When the following products are applied to exposed nerve elements

- Amniotic tissue or amniotic fluid
- adhesive
- steroid
- Platelet-rich plasma fluid
- Gel Foam
- Allograft tissue
- Fibrin Adhesive
- Dural patch

- 2) The subject (or legal representative) voluntarily wishes to discontinue the trial.
- 3) Surgery that may affect safety and efficacy evaluation, or when using other drugs and procedures in conjunction with other drugs and procedures
- 4) If an adverse event occurs during follow-up observation that makes it difficult to continue the clinical trial
- 5) Subjects who are not able to continue to follow up on the treatment of this clinical trial due to loss of contact during this clinical trial
- 6) Inclusion/exclusion criteria non-conformity confirmed since enrollment in the trial
- 7) If the principal investigator deems it inappropriate as a subject (if he does not comply with the investigator's instructions, if it is judged that he or she can no longer participate in the clinical trial in terms of safety or ethics due to a change in the subject's condition, etc.);

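### Section 14.2.2 item 1 stops a subject's trial after any serious adverse event, in conflict with 12.3(4); a subject who could have continued but is stopped before the week-6 MRI is lost from both efficacy sets

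*Combined protocol and SAP*

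**What the plan says.** Section 14.2.2 item 1, under the training heading, gives this rule: "In the event of a serious adverse event, the clinical trial of the subject shall be stopped". It does not depend on causality, recoverability or the investigator's view.

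Other parts of the protocol are conditional:

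- Section 12.3(4), repeated in the synopsis, is the subject-level dropout criterion: "If an adverse event occurs during follow-up observation that makes it difficult to continue the clinical trial". An SAE as such is not on the 12.3 list.
- Section 14.2.2 item 3 deals with subjects discontinued because of "adverse events or serious adverse events that make it difficult to proceed with the clinical trial". For them, "the application shall be stopped immediately".
- Section 12.1(2) uses similar wording, "adverse event/serious adverse event that makes it difficult to proceed with the clinical trial", and adds that the investigator decides. It stands in a list that mainly concerns stopping the trial or a site.

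Seriousness is defined broadly. Section 14.1.3 includes "Need to be hospitalized or need to extend the length of hospitalization", and note 2 to the schedule in 1.2 says: "If the hospital stay is prolonged or severe treatment is required due to the occurrence of surgical complications, it is reported as an SAE".

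Section 13.1 makes the PP Set the main population. PP membership requires FA membership and completion of the trial, and dropout is the first listed exclusion. FA membership requires a primary efficacy result. Section 13.2 leaves missing values uncorrected.

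**The concern.** The protocol gives two different answers for the same subject. Take someone whose stay is lengthened by a wound problem, who recovers and could attend Visit 4. Under 14.2.2 item 1 this subject's trial ends; under 12.3(4) it need not. Two sites could therefore treat the same event differently, and that choice decides who is in the main population.

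Stopping has no evident safety purpose here. The device is applied once, during surgery, so ending participation removes no exposure. Safety follow-up of the event is required separately, by 14.2.2 item 2 and 14.3.2. What the stop can end is the remaining scheduled assessments, including the MRI that supplies the primary endpoint. At stake are primary scores that could have been collected, in a trial planned with only 30 evaluable subjects per arm.

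**Working it through.** **Step 1: what is stopped.** Item 1 stops the subject's clinical trial; item 3 uses a separate word, application. Section 14.2.1 also codes action on the device as not applicable "in the case of single-application clinical trials", and this is such a trial. The end of participation is therefore the more natural reading of item 1, though the text does not spell it out.

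**Step 2: which rule applies.** Item 3 speaks of SAEs that make proceeding difficult, which presupposes that some SAEs do not. It mainly says what to do once a subject is discontinued, so the firmest contrast is between item 1 and 12.3(4). The two cannot both hold for an SAE from which the subject recovers well enough to continue.

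**Step 3: consequence for the analysis sets.** The primary endpoint is measured once, at the week-6 MRI (Visit 4, window ±2 weeks).

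- Stopped before that MRI, with none taken: no primary result, so not in the FA Set and hence not in the PP Set.
- An unscheduled MRI is possible under 10.3.5, but only if judged necessary.
- Section 12.4(3) includes dropouts in the analysis in principle, but provides no way to obtain the missing score.
- An SAE at or after the Visit 4 MRI costs little, because the score exists.

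**Step 4: reproduce the plan's power.** Inputs from 7.4: margin 0.57, SD 0.774 in both arms, true difference 0, one-sided alpha 0.025.

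Power = 1 − F(t; 2n − 2, λ), where F is the noncentral t distribution function, t is the 97.5% point of the central t on 2n − 2 degrees of freedom, and λ = 0.57 / (0.774 × √(2/n)).

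For n = 30: λ = 0.57 / (0.774 × 0.2582) = 2.85 on 58 degrees of freedom, and power = 0.80086. This equals the plan's figure. The dropout step also reproduces: 30 / 0.9 = 33.3, rounded up to 34 per arm.

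**Step 5: effect of losses beyond the allowance.**

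| Analysed per arm | Power | Loss (points) |
|---|---|---|
| 30 | 80.09% | 0 |
| 29 | 78.70% | 1.4 |
| 28 | 77.22% | 2.9 |
| 27 | 75.67% | 4.4 |

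**Step 6: a range under an assumed SAE rate.** The documents give none; 3% to 10% is an assumption.

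- Per arm: 34 × 0.03 = 1.0 to 34 × 0.10 = 3.4 subjects. Of the 69 enrolled: 2.1 to 6.9.
- If the 10% allowance already covers SAE stops, the loss is zero.
- If SAE stops act on those left after other dropout, the starting point is 34 × 0.9 = 30.6 per arm (power 80.9%). At 3%, 30.6 × 0.97 = 29.7 (79.7%); at 10%, 30.6 × 0.90 = 27.5 (76.5%).

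Step 6 counts every SAE as a lost score. The losses caused by item 1 are only those SAE subjects who could have continued, had no other reason to drop out, and were stopped before the MRI. That number cannot be derived from the documents.

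**The case against.** The sentence may never have operated as written. It sits under a training heading and refers to a section 17.3 that does not exist, which suggests unadapted template text. The governing list in 12.3 does not name SAEs, and the dedicated SAE section, 14.3.2, requires follow-up without any stop. The document is a loose translation, so stopped could mean a pause, after which the MRI might still fall inside its window. All of this stands: the loss arises only if item 1 is followed literally.

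The size is also open. Subjects too ill to continue would leave under 12.3(4) anyway. Some surgical complications, such as a dural tear, are already dropouts under 12.3(1). Nothing shows that SAE stops come on top of the 10% allowance. This too stands, and makes the figures in step 6 closer to upper bounds at each assumed rate.

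A further objection concerns the remedy. Under 9.5.2 the investigator cannot be blinded to treatment. Replacing an automatic rule with a judgement about difficulty gives that investigator influence over who stays in the main population. This is a fair criticism of aligning the wording and doing nothing else. The fix must therefore separate data collection and PP classification from that judgement.

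A reader might infer that the rule biases the non-inferiority comparison. That would need SAE stops at different rates by arm, and stopped subjects whose scar scores differ from the rest. The documents show neither. A reader might also infer that the trial is underpowered; that does not follow, because the loss may be zero.

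**Conclusion.** The inconsistency is real: item 1 is unconditional, while 12.3(4) and the wording of item 3 are not. Followed literally, item 1 would lose a primary score that could have been obtained from any SAE subject who was able to continue but was stopped before the week-6 MRI. Such a subject leaves the PP Set and also the FA Set, so the second population cannot recover the loss.

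The number of such subjects is unknown. The power loss is zero if they fall within the planned dropout allowance, and 1.4 to 4.4 points if one to three per arm come on top. These figures rest on the plan's own margin and SD and, for the range of subjects, on an assumed SAE rate of 3% to 10%. No bias and no effect on the error rate is established. This is a cheap improvement to the protocol and not a threat to the trial's conclusion. Confidence is medium, because the result depends on reading stopped as the end of participation.

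**What to change.** 1. Reword 14.2.2 item 1 so that an SAE ends participation only under the condition in 12.3(4), and state that an SAE alone is neither a dropout nor a PP exclusion.
2. Obtain the scheduled week-6 MRI (where safe), VAS and ODI in every consenting subject with an SAE, whatever the investigator decides about continuing. An available score then meets the FA requirement for a primary result under the existing 13.1 definition.
3. Have staff blind to arm decide and document PP status for every SAE subject before the assignment codes are released, and report each classification.
4. Correct the reference to 17.3 in the same item to 14.3.1. This is clerical.

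The cost is a protocol amendment with approval under 19.6. No visit, scheduled scan or subject is added. The synopsis reports that 69 subjects have been enrolled. If follow-up is complete, missed scans cannot be recovered and only step 3 is still useful. A change to PP membership this late carries its own risk, which is why the rule should be fixed blind to arm and before code release.
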